2.0 OBJECTIVES

2.1 Primary Objectives

Aim 1: Using our enhanced telehealth techniques, determine if **patient activation**, self-efficacy, ostomy-related knowledge, and HRQOL will be improved and sustained over time in the online interactive communication Ostomy Self-Management Telehealth program (OSMT) curriculum compared to a usual care (UC) group.

Hypothesis 1.1: Taking into account time since surgery:

- 1.1.1 Survivors in the OSMT group will have greater improvement in **patient activation** compared to UC.
- 1.1.2 Survivors in the OSMT group will have a sustained improvement in **patient activation**.
- 1.1.3 In survivors in the OSMT group, higher attendance levels will be associated with increased **patient activation**.

Hypothesis 1.2: Taking into account time since surgery:

- 1.2.1 Survivors in the OSMT group will have greater improvement in **self-efficacy, ostomy-related knowledge, and HRQOL** compared to UC.
- 1.2.2 Survivors in the OSMT group will have a sustained improvement in **self-efficacy, ostomy-related knowledge, and HRQOL**.
- 1.2.3 In survivors in the OSMT group, higher attendance levels will be associated with increased **self-efficacy, ostomy-related knowledge, and HRQOL**.

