5.0 ELIGIBILITY CRITERIA

5.1 Eligibility criteria

1. Cancer survivors over 21 years of age having undergone a procedure that needed an intestinal stoma (fecal or urinary). Survivors with temporary ostomies will be included.
2. All participants must have a full understanding of the protocol and be able to sign an informed consent form.
3. Having an identified caregiver is **not** a requirement for eligibility.
4. All participants will attend their first training session at least six weeks after their operation.
5. There is no maximum time since surgery.

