6.0 STRATIFICATION FACTORS

Potential stratification factors are gender, medical center site, and fecal vs. urinary ostomy. Gender and site will be stratified in the randomization process, whereas ostomy type will be explored in the analysis.

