12.0 STATISTICAL CONSIDERATIONS

12.1 General. Aim 1 will be analyzed with linear mixed models for repeated measures. Aim 2 will utilize a variety of sources and methods to enumerate the intervention program and ostomy-related family resources in each study arm.

If a subject misses Session 3 or Session 4 or both, they can make up the missed session(s) with the next 1 or 2 scheduled groups. If they miss both chances to make up the sessions, they

will be asked to do the surveys and will be analyzed as a separate group using an intent-to-treat contrast.

12.2 Aim 1: Using our enhanced telehealth techniques, determine if **patient activation**, self-efficacy, ostomy-related knowledge, and HRQOL will be improved and sustained over time in the online interactive communication Ostomy Self-Management Telehealth program (OSMT) curriculum compared to a UC group.

Under an intent-to-treat approach, change in outcomes will be evaluated longitudinally with linear mixed models, testing the effect of study arm adjusted for potential confounders. Such models evaluate both associations and rates of change, accounting for within-subject correlation. The Primary Outcome will be PAM. Secondary Outcomes include SE, COH-QOL-CRC scales, and Ostomy Knowledge. Post hoc contrasts will evaluate effect of training (baseline to post) and whether effect is sustained after training (6 month post to follow-up). Standard multivariable modeling procedures will be used to select or eliminate potential confounding variables, starting with candidate variables that are biologically plausible or found to be associated with endpoint change scores (baseline vs. follow-up) in bivariate analyses with a p-value of less than 0.20. Potential candidate covariates and confounders include (but are not limited to) CG participation in training sessions, depression (HADS), time since surgery, ostomy type, age, sex, stage, anticipated permanence of ostomy, and pre- or post-surgical radiation or chemotherapy. We will explore potential interaction for plausible effect modifiers, such as gender, or having a CG.

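### Time since surgery, which Hypotheses 1.1 and 1.2 condition on, can be selected out of the Aim 1 models, and the randomization strata are not fixed terms either

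*Protocol*

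**What the plan says.** Eligibility (Protocol 5.1) has a floor and no ceiling: "All participants will attend their first training session at least six weeks after their operation" and "There is no maximum time since surgery". Protocol 2.1 opens its two sets of Aim 1 hypotheses with "Hypothesis 1.1: Taking into account time since surgery" and "Hypothesis 1.2: Taking into account time since surgery". Each set covers a between-arm comparison, a sustained effect within the OSMT arm, and an association with attendance.

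Protocol 12.2, repeated in the SAP under Aim 1, gives the covariate rule: "Standard multivariable modeling procedures will be used to select or eliminate potential confounding variables". A variable may start as a candidate because it is biologically plausible, or because it is "found to be associated with endpoint change scores (baseline vs. follow-up) in bivariate analyses with a p-value of less than 0.20". Time since surgery appears only in the candidate list: "Potential candidate covariates and confounders include (but are not limited to) CG participation in training sessions, depression (HADS), time since surgery, ostomy type". Sex comes later in that list. Site is not in it.

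On randomization, Protocol 6.0 says "Gender and site will be stratified in the randomization process", and 7.2.2 describes separate lists by site and gender in blocks of four. The power statement in 12.13 assumes adjustment for baseline and names no other covariate. The attendance models in 12.2 and the SAP have a weighted attendance score as an independent variable, with no covariates named.

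**The concern.** The hypotheses handle a very wide entry population by conditioning on time since surgery, and the analysis section does not make that conditioning binding. The documents themselves give reason to think the variable is prognostic. Protocol 3.0 describes bowel and bladder adaptation over weeks and months. Protocol 4.0 reports that 18% of participants in an earlier study took at least a year to feel comfortable with their ostomy care or never did.

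Three things are at stake. First, a result could be reported for Hypothesis 1.1.1 from a model that does not test it as worded. Second, the covariates of the primary model would be settled after their association with outcome change has been examined. Third, design information is not used: the strata that shaped the allocation have no guaranteed place in the model.

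**Working it through.** **Text check.** The plan gives no figure for the effect of these covariates, so there is nothing to reproduce. Set side by side, the sections show the following:

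- Time since surgery: a condition in 2.1, unbounded above in 5.1, a candidate open to elimination in 12.2 and the SAP.
- Gender: a stratum in 6.0 and 7.2.2, an optional candidate (as sex) in 12.2 and the SAP.
- Site: a stratum in 6.0 and 7.2.2, not named in 12.2 or the SAP.
- No section forces any of the three into an Aim 1 model.

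**Could time since surgery drop out?** Take 150 completers (75 per arm, 12.13) and let r be its true correlation with the change score (assumed). By Fisher's z, the chance of missing p < 0.20 is about Φ(1.282 − atanh(r) × √147), less a negligible opposite tail. This is 52% at r = 0.10, 29% at r = 0.15 and 12% at r = 0.20. These figures apply to the p-value route only. Entry as biologically plausible avoids the screen but not later elimination.

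**Cost to the arm comparison.** Inputs are alpha 0.05 (12.13; two-sided assumed, since sidedness is not stated), 80% power for the adjusted test (1.960 + 0.842 = 2.802), and R², the share of residual variance explained by the omitted terms. R² is assumed, because the documents give none.

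*Strata omitted.* Stratified allocation has already removed R² from the true variance of the arm difference, but the model still counts it, so the reported z is the true z times √(1 − R²). Hence:

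- actual alpha = 2 × [1 − Φ(1.960/√(1 − R²))]
- power = Φ(2.802 − 1.960/√(1 − R²))

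*Time since surgery omitted.* It was not stratified, so the true variance is itself larger. The standard error rises by 1/√(1 − R²) − 1, and power = Φ(2.802 × √(1 − R²) − 1.960).

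| Assumed R² | Alpha, strata omitted | Power, strata omitted | SE increase, time omitted | Power, time omitted |
|---|---|---|---|---|
| 0.02 | 0.048 | 79.4% | 1.0% | 79.2% |
| 0.05 | 0.044 | 78.5% | 2.6% | 78.0% |
| 0.10 | 0.039 | 76.9% | 5.4% | 75.7% |

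For R² = 0.10, √0.90 = 0.949 and 1.960/0.949 = 2.066. Alpha is 2 × [1 − Φ(2.066)] = 0.039. Power is Φ(0.736) = 76.9% with the strata omitted, and Φ(2.802 × 0.949 − 1.960) = Φ(0.698) = 75.7% with time omitted.

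**Dependence on model form.** The table applies when the baseline outcome is a covariate, as 12.13 suggests. Section 12.2 speaks of change evaluated longitudinally, with a baseline-to-post contrast, and this can also be read as keeping baseline as a response. In that model the main effect of a time-constant covariate shifts all visits equally and, with complete data, cancels from the arm contrast in change. The covariate then gains precision only if it also enters by visit.

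**Attendance models.** Attendance within the OSMT arm is not randomized. If time since surgery is related to both attendance and outcome change, leaving it out biases the attendance coefficient. The documents give no figure from which to size this.

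**The case against.** The strongest reply is that little is at risk in the randomized comparison. Arms are allocated at random within site and gender, so leaving these variables out does not confound the arm effect, and leaving out balanced strata makes the test conservative. That stands. A reader might infer bias or an inflated false-positive rate in the arm comparison from the omission. The documents do not support that reading, and the calculation points the other way.

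It can also be said that the hypothesis wording does not promise a term in every model, that time since surgery can enter on plausibility alone, and that 12.11 promises further control of confounding by regression. These points show that the variable may well be used. They do not show that it must be, because the same rule allows elimination and no section exempts it.

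Site is unlisted, which is not the same as excluded, because the candidate list is expressly open. What is missing is a commitment fixed in advance.

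Three further readings go too far. The plan does not specify a straight-line term for time since surgery, and no document gives its distribution, so there is no basis for faulting linearity or prescribing a log scale. The documents do not say that selection is run separately for each outcome. Nor do they say that recently operated participants change most. Finally, 12.2 makes PAM the primary outcome, so Hypothesis 1.2 is primary only by its place under the Primary Objectives.

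**Conclusion.** The point holds as a disagreement between the stated hypotheses and design on one side and the covariate rule on the other. The rule can yield a primary PAM model without the variable that Hypothesis 1.1 names and without the randomization strata, and that model would be settled after outcome data are examined.

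The statistical cost to the arm comparison is modest. At assumed R² of 0.02 to 0.10, about 1 to 3 points of power are lost from the strata, or about 1 to 4 points if the same share is due to time since surgery. These sizes rest on the assumed R², a two-sided test and a model with baseline as a covariate. Under a baseline-as-response model with main effects only, the precision cost is essentially nil. The textual mismatch remains under either model.

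The one place where bias is possible is the attendance hypotheses, 1.1.3 and 1.2.3, and its size is unknown. The plan should be changed, mainly because the change is nearly free.

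**What to change.** In Protocol 12.2 and the SAP, state the following:

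1. Time since surgery at baseline, site and gender are fixed terms in every Aim 1 between-arm model and are not subject to selection. The functional form for time since surgery is set before outcome data are examined.
2. The between-arm model adjusts for the baseline outcome, as 12.13 assumes. If baseline is instead kept as a response, the three terms also enter by visit.
3. Time since surgery is likewise retained in the within-arm models for sustained effect (1.1.2, 1.2.2) and in the attendance models (1.1.3, 1.2.3).
4. Data-driven selection is confined to the remaining baseline candidates or to sensitivity analyses.

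The cost is a few sentences and a few degrees of freedom: two for the three sites, one for gender, and one for time since surgery if it enters as a single term (more for a flexible form or terms by visit). At least 75 completers per arm are planned. The surgery date must be recorded for every participant. Applying the six-week criterion and listing the variable as a candidate already imply this, but it is worth confirming that a study form captures the date itself.

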7.2.2 Randomization

Patients who meet eligibility criteria will be approached to enroll in the randomized telehealth intervention versus a usual care comparison group using an approved consent process (see Schema). **Consents will need to be signed and received prior to randomization.**

Subjects will be randomized using stratified permuted block randomization. Once consented, the participant will be randomized to OSMT or UC, using computer-generated random lists blocked by site and gender, and with assigned arm in sealed envelopes blind to investigators and coordinators until assignment. This means that each participating site will have a unique pair of computer-generated randomization lists, one for male and the other for female, ensuring balance by sex between intervention and usual care groups at each site without the need for communication with a data coordinating center core for each randomization. The randomization lists will be comprised of blocks of 4 with permuted patterns so that balance is achieved after multiples of 4 in each sex have been randomized.

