**Statistical Analysis Plan**

## Statistical Analysis Plan

**General.** Aim 1 will be analyzed with linear mixed models for repeated measures. Aim 2 will utilize a variety of sources and methods to enumerate the intervention program and ostomy-related family resources in each study arm.

**Aim 1:** Using our enhanced telehealth techniques, determine if **patient activation**, self-efficacy, ostomy-related knowledge, and HRQOL will be improved and sustained over time in the online interactive communication Ostomy Self-Management Telehealth program (OSMT) curriculum compared to a UC group.

Under an intent-to-treat approach, change in outcomes will be evaluated longitudinally with linear mixed models, testing the effect of study arm adjusted for potential confounders. Such models evaluate both associations and rates of change, accounting for within-subject correlation. The Primary Outcome will be PAM. Secondary Outcomes include SE, COH-QOL-CRC scales, and Ostomy Knowledge. Post hoc contrasts will evaluate effect of training (baseline to post) and whether effect is sustained after training (6 month post to follow-up). Standard multivariable modeling procedures will be used to select or eliminate potential confounding variables, starting with candidate variables that are biologically plausible or found to be associated with endpoint change scores (baseline vs. follow-up) in bivariate analyses with a p-value of less than 0.20. Potential candidate covariates and confounders include (but are not limited to) CG participation in training sessions, depression (HADS), time since surgery, ostomy type, age, sex, stage, anticipated permanence of ostomy, and pre- or post-surgical radiation or chemotherapy. We will explore potential interaction for plausible effect modifiers, such as gender, or having a CG.

The COH QOL-CRC assesses ostomy burden and care abilities, including time taken to perform daily ostomy care, comfort with ostomy care, comfort with diet, adjustment of diet for ostomy, appetite, clothing and other problems with ostomy placement. We will also measure clinically related outcomes, including medical attention for problems with bowel, bladder, or ostomy. Changes in these responses will be compared between treatment groups with linear mixed models, chi-square tests or t-tests, as appropriate.

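### Caregiver attendance at OSMT sessions, which occurs after randomisation and only in OSMT, is a candidate confounder for the intent-to-treat test of arm

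*Protocol*

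**What the plan says.** Protocol 12.2 describes intent-to-treat linear mixed models "testing the effect of study arm adjusted for potential confounders". Candidates enter if they are biologically plausible or reach p<0.20 in a bivariate test against the baseline-to-follow-up change score. After that, "Standard multivariable modeling procedures will be used to select or eliminate potential confounding variables"; no threshold for elimination is given. The list begins "Potential candidate covariates and confounders include (but are not limited to) CG participation in training sessions, depression (HADS), time since surgery", and the SAP repeats it ("CG participation in training sessions, depression (HADS), time since surgery").

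The next sentence treats caregiver availability as a separate matter: "We will explore potential interaction for plausible effect modifiers, such as gender, or having a CG". The listed covariate is therefore attendance, not having a caregiver.

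The list serves all of Aim 1. That includes the between-arm Hypotheses 1.1.1 and 1.2.1 ("Survivors in the OSMT group will have greater improvement in" the named outcomes compared with UC) and the within-OSMT Hypotheses 1.1.2, 1.1.3, 1.2.2 and 1.2.3. Neither document limits candidates to pre-randomisation variables or confines this one to OSMT-only models.

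**The concern.** A confounder of a randomised comparison has to precede randomisation. Caregiver attendance does not.

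- **Timing.** Section 7.2.2: "Once consented, the participant will be randomized to OSMT or UC". The caregiver session comes after Session 2, and caregivers are invited again to Session 4 (session table in 9.2.5).
- **Part of the treatment.** Section 9.2.4 counts a caregiver session and a joint session in the OSMT curriculum.
- **Self-selected.** Some participants will have no caregiver (9.2.5), and a missed caregiver session need not be made up (8.1).
- **Absent from UC.** The UC package in 9.1 contains no sessions, and 7.2.5 describes session payments only for caregivers of intervention subjects.

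Adjusting for attendance removes whatever benefit runs through caregiver involvement. It also brings in any difference between subjects whose caregivers attend and those whose caregivers do not. At stake is the primary PAM comparison, which could then not be reported as the intent-to-treat effect.

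**Working it through.** **Inputs.** From 12.13: PAM SD 13, within-subject correlation r = 0.60, two follow-ups, alpha 0.05 (taken as two-sided), effect 2.75, up to 120 per arm with 15% dropout, so 120 × 0.85 = 102 per arm. Assumed, because the documents are silent: OSMT caregiver participation p = 40–60%, and a gap g of −4 to +4 PAM points (OSMT subjects with minus without a participating caregiver, at follow-up given baseline).

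**The plan's own figure.** Detectable difference = (1.960 + 0.842) × 13 × √f × √(2/n). With f = (1 − r²)/2 = 0.32 and n = 75 this is 3.36, against 3.4 in the table. Under compound symmetry the factor for the mean of two follow-ups adjusted for baseline is f = (1 + r)/2 − r² = 0.44. Both factors are used below.

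**Baseline as covariate, CG participation retained.** It is zero throughout UC, so the arm coefficient is the adjusted OSMT mean without a participating caregiver minus the UC mean.

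- Estimate = true effect − p × g. From 2.75, at g = +2 to +4: 1.95 to 1.15 (p = 40%) or 1.55 to 0.35 (p = 60%). At g = −2 to −4: 3.55 to 4.35 or 3.95 to 5.15. At g = 0 there is no shift.
- Variance ratio = [1/n + 1/(n(1−p))] ÷ (2/n) = (2−p)/(2(1−p)) = 1.33 (p = 40%) or 1.75 (p = 60%).
- SE without CG = 13 × √(2f/102) = 1.21 (f = 0.44) or 1.03 (f = 0.32). With CG it is 1.39–1.60 or 1.19–1.36.

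**Baseline as a repeated response.** In 12.2, "Such models evaluate both associations and rates of change" and the baseline-to-post contrast allow this reading. Exact GLS with three visits, compound symmetry 0.60 and CG as a main effect only leaves the arm-by-time contrast at 2.75 with SE 1.41, with or without CG. If the arm means are also constrained equal at baseline (an assumed variant), g = +2 to +4 gives 2.58–2.41 (p = 40%) or 2.54–2.34 (p = 60%), and the SE rises from 1.21 to 1.25–1.28. A CG-by-time term, which neither document mentions, would bring back 1.15/0.35 at g = +4.

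**How often it would be retained.** Simulation of the baseline-as-covariate model: 4,000 runs per scenario, 102 per arm, compound symmetry, true effect 2.75. Entry means p<0.20 in a pooled bivariate test on change to 6 months. The elimination step (p<0.05 in the multivariable model) is assumed. Cells show p = 40%/60%.

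| Gap | Kept: entry only | Mean estimate | Power | Kept: with elimination | Mean estimate | Power |
|---|---|---|---|---|---|---|
| 0 | 35/44% | 2.61/2.52 | 54/45% | 3/3% | 2.73/2.70 | 62/61% |
| +2 | 62/68% | 2.09/1.70 | 36/23% | 19/20% | 2.42/2.20 | 51/49% |
| +4 | 84/85% | 1.25/0.51 | 16/9% | 60/59% | 1.49/0.90 | 27/25% |
| −4 | 29/20% | 3.32/3.26 | 72/68% | 24/13% | 3.28/3.18 | 71/68% |

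Power without CG is 59–63% in these runs. Simulation error is about 1.5 percentage points, and 0.05 on means. At gap 0 the variable still passes the screen in 35–44% of runs: it occurs only in OSMT, so it also marks arm, and a working intervention helps it through.

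**No true effect.** Under either retention rule, two-sided rejection is 14–20% at gap ±4, 5–8% at ±2 and 4–5% at 0. A positive gap pushes the estimate against OSMT. A gap of −4 gives a spurious mean benefit of 1.10/1.46 (entry only) or 0.98/1.30 (with elimination).

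**The case against.** There are four serious counter-arguments.

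1. **The harm depends on the model.** The language of 12.2 fits baseline as a repeated response at least as well as baseline as a covariate, and with a CG main effect the arm-by-time contrast is then untouched. The baseline-adjusted description comes from 12.13, where it concerns the power estimates. This stands, and it makes the harm conditional. It does not remove the problem, because nothing in either document commits to the safe model.

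2. **Retention is only possible.** The variable is one candidate that may be eliminated, and its UC value might be recorded as not applicable, which would keep it out of an arm model. The first part stands. The second relies on a coding convention that the plan does not state.

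3. **The numbers rest on assumptions.** The participation rate and gap are assumed. Rejection of 14–20% needs a gap larger than the 2.75 effect itself. The simulated rule leaves out the plausibility route and adds an elimination threshold. The 59–63% starting power has nothing to do with caregivers: it follows from using 102 per arm with f = 0.44. All of this stands, so the retention rates are illustrations and not forecasts. Leaving out the plausibility route, if anything, understates entry. The shift −p × g and the variance factor do not depend on the simulation.

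4. **The fix could reach too far.** It might be read as barring the separate missed-session group in 8.1 and 12.1, or the interaction with having a caregiver. A sentence confined to adjustment covariates leaves the first alone. The second survives if caregiver availability is recorded before randomisation.

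**Conclusion.** The concern holds. Both documents allow a post-randomisation, OSMT-only component of the intervention to be used as a confounder in the test of arm. If it is retained in a baseline-adjusted model, the arm coefficient is not the intent-to-treat effect. It shifts by −p × g in either direction, and its variance is multiplied by (2−p)/(2(1−p)). For assumed participation of 40–60% and gaps of −4 to +4, a true 2.75 becomes anything from 0.35 to 5.15, with variance up 1.33- to 1.75-fold. With baseline as a response and a CG main effect only, there is no harm to the arm-by-time contrast. The defect in the text is certain; the size of its effect depends on the model chosen, on retention, and on two quantities that the documents do not give. It should be fixed before analysis.

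**What to change.** Add one sentence to the covariate paragraph of protocol 12.2 and the same sentence to the SAP: caregiver participation in training sessions, and any other variable arising after randomisation, will not be used as an adjustment covariate in the between-arm models (Hypotheses 1.1.1 and 1.2.1). Examine caregiver participation only within OSMT, alongside the planned attendance analysis, and describe that analysis as observational.

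Two consequences follow. The HADS score, collected at all three survey times (8.2), would enter the arm models only at its baseline value. For the interaction with having a caregiver, availability should be recorded before randomisation, since 7.2.3 has caregivers designated at registration and 7.1 allows registration up to the first session.

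The cost is the one sentence in each document. No new data are needed and no planned question is lost.

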The focus of Aim 2 is to compare medical care utilization, patient burden, and impact on patient time and activities for individuals participating in OSMT with those receiving UC. Assessment of these measures is critical for patient-centered care, in order to minimize the financial burdens and non-financial impacts (e.g., time commitment) of new interventions. To address hypotheses 2.1 and 2.2, we will collect detailed information on use of medical care services and supplies related to ostomy care, patient burden for these services and supplies, required patient and caregiver time for ostomy care, interference with employment and volunteer activities, and perceived financial burden. Details regarding the four types of information to be collected for Aim 2 are presented below. We also provide information on assessment on study activities to address replication of the OSMT intervention (Question 2.2).

12.4 Ostomy-Related Medical Care Supplies and Services. We will collect information from study participants on their use of supplies and services related to ostomy care and their out-of-pocket expenses for these supplies/services. Ostomy-related services/supplies will be categorized in two separate groups:

- Medical care encounters and ostomy supplies including: OCN visits; other ostomy-related medical care encounters (including physician and ED visits); surgical revision of stoma; ostomy appliances, wafers, bags; bowel medications; and skin medications.
- Other equipment, household modifications related to ostomy and ostomy care, including: waterproof covers on for mattresses and furniture; bathroom remodels to accommodate ostomy care; special clothing to cover ostomy bag; alteration of clothing to cover ostomy bag, and transportation to and parking for ostomy-related medical care.

12.5 Ostomy-Related Time Requirements. We will also collect ostomy-related time requirements, that is, patient time required to obtain ostomy care, perform ostomy bag and wafer management, and clean ostomy bag spills. We will also ask study participants about use of both formal and informal CGs, time for caregiving activities related to ostomy care, and types of assistance (e.g., with housekeeping and shopping) required due to ostomy and ostomy care.

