12.6 Employment/Volunteering Effects. All participants will be asked about their current employment status and volunteer activities (including usual hours per week devoted to work and volunteering). All subjects will be asked if their ostomy-related management and health problems led to work-loss days, sick leave days, leave without pay, changes in amount of hours worked and/or volunteered, loss of employment or volunteer opportunity, job-related corrective actions, and impaired job search and/or volunteer activities.

12.7 Perceived financial burden. The financial impact of ostomy and ostomy care will likely reflect patient burden for ostomy services and supplies as well as patient and caregiver time and interference with employment. Patients will be requested to provide information on perceived financial burden associated with ostomy-related care and on deferral of doctor visits and medication pick-up/refills because of financial pressures.

Information for Aim 2 will be collected using a self-administered patient questionnaire. (Appendix D)

12.8 OSMT Intervention Replication Model. Disseminating/replicating our OSMT intervention program requires: 1) an intervention operations manual; 2) official versions of all

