\$0 \$1-\$5 \$6-\$10 \$11-\$15 \$16-\$25 \$26-\$50 \$51-\$100 \$101+

31. Do you make some or all your own clothes because you have an ostomy and nothing in the clothing stores will fit you appropriately?

- a. No → **IF NO**, skip to Question 32 below.
- b. Yes → **IF YES**, how much do you spend to make your own clothes in a year?
\$0 \$1-\$5 \$6-\$10 \$11-\$15 \$16-\$25 \$26-\$50 \$51-\$100 \$101+

32. Did you purchase any fashion accessories specifically made for someone with an Ostomy (for example, fashion wraps, special underwear, Stealth belt)?

- a. No → **IF NO**, skip to Question 33 below.
- b. Yes → **IF YES**, how much did you spend to purchase your special underwear/girdle/body wrap?
\$0 \$1-\$5 \$6-\$10 \$11-\$15 \$16-\$25 \$26-\$50 \$51-\$100 \$101+

33. Do you wear a hernia belt?

- a. No → **IF NO**, skip to Question 34 below.
- b. Yes → **IF YES**, how much did you spend to purchase your hernia belt(s)?
\$0 \$1-\$5 \$6-\$10 \$11-\$15 \$16-\$25 \$26-\$50 \$51-\$100 \$101+

34. How would you describe your current employment?

(Please select only one)

- Full time
- Part time
- Retired and not working another job
- Home maker
- Temporarily laid off
- Unemployed and looking for work
- Unemployed and **not** looking for work
- On disability

Other: (please explain) _____

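### Sections 12.4 to 12.7 promise Aim 2 data on work loss, volunteering, deferred care, caregiver time, stoma revision and bathroom remodelling that the scheduled burden surveys, as shown, do not collect

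*Protocol*

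**What the plan says.** Section 12.3 of the Protocol says that four types of information will be collected for Aim 2 and ties them to Hypotheses 2.1 and 2.2. Sections 12.4 to 12.7 then list them.

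- **12.4, supplies and services.** The list includes surgical revision of the stoma and "bathroom remodels to accommodate ostomy care".
- **12.5, time.** Besides the patient's own time, participants will be asked about formal and informal caregivers, "time for caregiving activities related to ostomy care", and help such as housekeeping and shopping.
- **12.6, employment and volunteering.** "All subjects will be asked if their ostomy-related management and health problems led to work-loss days, sick leave days, leave without pay". The list goes on to changed hours, lost employment or volunteer roles, corrective action and impaired job search. Usual weekly hours of work and volunteering are also promised.
- **12.7, perceived financial burden.** "Patients will be requested to provide information on perceived financial burden associated with ostomy-related care", and also "on deferral of doctor visits and medication pick-up/refills because of financial pressures".

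Section 12.7 closes by naming a self-administered questionnaire, Appendix D, as the source for Aim 2. Section 11 assigns productivity losses, caregivers and paid housekeeping to the Burden of Ostomy Care survey. Section 8.2 schedules that survey as Appendix 7a at baseline and 6 months, and as Appendix 7b at the end of sessions. The SAP repeats a general sentence on Aim 2 and names no instrument for it.

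**The concern.** The promise is firm and covers all subjects, but the forms that section 8.2 tells sites to send do not appear to carry the questions. Section 12.7 itself expects the financial impact to reflect patient and caregiver time and interference with employment. If the forms are used as shown, caregiver time and employment interference are not measured. A reported difference in family financial burden would then describe something narrower than the plan says it describes. Baseline reports of hours, lost days and helper time cannot be recovered reliably at the end of the study.

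**Working it through.** No formula applies: the plan gives no power statement or target figure for Aim 2. The check sets each promised element beside the survey items shown. Appendix 7a is numbered continuously from 1 to 34, and 7b from 1 to 12.

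| Promised (section) | Nearest item shown | Gap |
|---|---|---|
| Stoma revision (12.4) | 7a Q2 to Q4 and Q11 to Q13: nurse, physician, emergency and urgent care contacts | No item on revision surgery |
| Bathroom remodelling (12.4) | 7a Q29 to Q33: covers, clothing, accessories, hernia belt | No item |
| Caregiver time; housekeeping and shopping help (12.5) | 7a Q27 and 7b Q11: whether help is received and from whom | No amount of time; no housekeeping or shopping |
| Work hours and work loss (12.6) | 7a Q34: "How would you describe your current employment", one choice from a list | No hours, lost days, leave or link to the ostomy |
| Volunteering (12.6) | None | No item |
| Deferred visits and refills (12.7) | None | No item |
| Perceived financial burden (12.7) | None in 7a or 7b | Cannot be settled (see below) |

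Count: 6 of the 7 groups have no matching item in the text shown, and 1 is open.

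**Other forms.** The baseline form in Appendix 2a adds household income. The self-efficacy survey asks how confident people are of getting help with chores, not whether they use it. Section 7.2.3 limits caregiver information to age, gender, relationship and work status, so it supplies no caregiving time.

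**What cannot be seen.** Section 8.2 gives the COH-QOL-CRC 43 scaled items. The text of Appendix 2b goes from item 6 to item 29, so 28 − 7 + 1 = 22 of the 43 items (51%) are not visible. A 0 to 10 rating of financial burden could sit there. Section 8.2 also cites a Greatest Challenge portion of 7a, and the form as shown ends at Q34 without it.

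**Appendix D.** Section 12.12 puts the Greatest Challenge question at the end of Appendix D, under a title that no listed appendix bears. Section 8.2 puts it in 7a. So Appendix D is either 7a under another label or version, or a separate questionnaire that section 8.2 never schedules. On neither reading would sites following 8.2 with the forms shown collect these data.

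**Reach.** Section 12.13 allows up to 240 participants. With 7a given twice, at most 240 × 2 = 480 completed forms are affected.

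**The case against.** The strongest reply is that part of the paperwork cannot be seen. This has force for two elements. Perceived financial burden might be among the unseen COH-QOL-CRC items, and further employment or deferral questions might follow 7a Q34. A reader might therefore infer that no survey anywhere in the protocol has an item on these outcomes; the documents do not support so absolute a statement. The reply is weaker for stoma revision, bathroom remodelling and caregiver time. These would naturally sit among the encounter, household and helper questions, where the numbering of 7a is unbroken.

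A reader might also infer that Question 2.1 cannot be answered at all. That goes too far. Appendix 7a asks about out-of-pocket costs for nurse, physician, emergency and urgent care visits, travel to in-person visits, appliances, covers, clothing and belts. Much of the patient's own time is covered too (Q8, Q24, Q26, Q28 and travel times). Question 2.1 is answerable in part.

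A third inference is that participants' time in the OSMT programme, needed for Question 2.2, goes unrecorded. No survey item shown asks it, but attendance is taken at each session (9.4), sessions last 1.5 to 2 hours (9.2.4), staff templates capture webinar and contact time (12.8), and peers log calls (9.2.1). Session time can largely be derived.

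Finally, the general statement in 12.1 and the SAP that Aim 2 uses a variety of sources might suggest data from elsewhere. However, 12.4 to 12.7 describe participants' reports, and 12.7 names a self-administered questionnaire.

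**Conclusion.** The mismatch is real in this form. Sections 12.4 to 12.7 promise six groups of data for which the scheduled burden forms, as shown, have no item beyond employment status and helper identity, and the questionnaire they cite is not among the numbered appendices. The effect is not confined to Question 2.1:

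- Hypothesis 2.1 loses caregiver time, household help and remodelling.
- Hypothesis 2.2 loses stoma revision.
- Question 2.1 loses employment effects and cost-related deferral, which leaves mainly out-of-pocket costs.

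This rests on two assumptions: that sites use the forms as shown, and that no relevant items were lost from the text after 7a Q34. Whether perceived financial burden is measured needs confirmation. Aim 2 is secondary and the primary outcome, PAM, is untouched, so this is a point that should be fixed rather than one that must be.

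**What to change.** 1. Identify Appendix D, state whether it is Appendix 7a, and correct the references in 12.7 and 12.12. If it is a separate form, include it and schedule it in 8.2.
2. If the items are not on the administered form, choose one of two routes:
   - Add short items to 7a at baseline and 6 months in both arms: usual work and volunteer hours; days lost and job or role changes because of the ostomy; visits or refills deferred for cost; helper hours, including housekeeping; stoma revision; and cost of bathroom modification.
   - Delete the unmeasured components from 12.4 to 12.7, align section 11, and restrict the Aim 2 conclusions to what is measured.
3. Check COH-QOL-CRC items 7 to 28 and any text after 7a Q34 for a measure of perceived financial burden. If there is none, add one rating or remove the outcome.

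The cost is about 8 to 10 short self-report items, a few minutes per participant, and a minor amendment. People already past baseline would have follow-up data only on the new items. For them, the comparison between arms at 6 months could not be adjusted for baseline and would probably be less precise; the analysis should say so.
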